7.7 Rophylactic Medications, Treatments, and Procedures

Not applicable.

7.8 Rescue Medications, Treatments, and Procedures

Not applicable.

7.9 Participant Access to Study Agent at Study Closure

Not applicable.

8 Assessment of Safety

8.1 Specification of Safety Parameters

8.1.1 Definition of Adverse Events (AE)

Adverse event (AE) refers to all adverse medical events that are observed in the subjects after receiving the investigational drug. These events may manifest as symptoms, signs, diseases or abnormal laboratory test results, but may not have a causal relationship with the investigational drug.

8.1.2 Definition of Serious Adverse Events (SAE)

Serious adverse event (SAE) refers to adverse medical events that lead to death, life-threatening results, permanent or serious disability or loss of function, or hospitalization or prolonged hospitalization in the subjects after receiving the investigational drug or congenital abnormalities or birth defects.

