5.4 Premature Termination or Suspension of Study

According to CTCAE (5.0), the clinical trial should be terminated if over one half of the subjects have grade 2 or greater investigational drug-related AEs or if one case of investigational drug-related SAE is observed.

- Major errors are identified in the clinical trial protocol during the trial, which render drug evaluation difficult.
- Termination requested by the sponsor under the premise that the interests and safety of the subjects are fully guaranteed.
- Trial termination ordered by the NMPA or Ethics Committee due to some tests.
- Inability to recruit patients.
- Lack of imaging even after dose adjustment.

Regardless of whether the trial is terminated by the sponsor or the investigator,

- The investigator should return all investigational drugs, eCRF and relevant trial materials to

the sponsor.

- The sponsor or the investigator should provide a written statement on the reason for early trial termination and inform all principal investigators related to this trial, the Ethics Committee, and NMPA as soon as possible. In addition, all subjects should be informed of the termination of the trial.

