- 4) After the dose escalation of all dose groups is completed, the imaging expert committee and the principal investigator will decide whether to continue enrolling 3-4 subjects in a certain initially identified optimal dose group for further exploration.

Security:

The principal investigator determines whether to increase the dose from the perspective of safety. Dose escalation should be stopped if one of the principles happen:① at least half of subjects in a dose group experience CTCAE grade 2 (or moderate) or above adverse reactions;② or at least 1/3 subjects experience CTCAE grade 3 (or severe) or above adverse reactions;③ or one serious adverse reaction in certain group.

The dose escalation will be determined by the principal investigator based on both imaging and safety results. During the clinical trial, based on the principle of subject protection, the dose group can be rapidly escalated to the subsequent dose group if nonvisualization or the above safety events happens after only one subject enrolled according to the investigator's discretion.

[figure not shown]

Figure 3 Dose escalation

After the dose escalation of all dose groups is completed, the imaging expert committee and the principal investigator will decide whether to enroll another 3 or 4 patients in the identified optimal dose group.

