7.3.2 Baseline Period

D-1

- 1) Review compliance with inclusion/exclusion criteria for the second time
- 2) Enrollment (Subjects can be enrolled in the relevant department due to primary tumor before D-1 and after D1 and complete the trial period during hospitalization) .
- 3) Record concomitant medications.

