7.3.4 Safety Follow-up Period

D6 to D28

- 1) Anti-SNA002 antibody: Blood samples are collected on $D6 \pm 1$ d, $D28 \pm 2$ d and sent to the central laboratory for detection.
- 2) Laboratory examination: blood routine, blood biochemistry, coagulation, and electrolyte tests were conducted on $D6 \pm 1$ d.

- 3) 12-lead ECG: detected on D6 ± 1d.
- 4) Distribute diary cards during the safe follow-up period of D6 ± 1 days (if the subjects discharge immediately after biopsy, the diary cards will be distributed on the day of discharge; if the subjects are not hospitalized, the diary cards will be issued after completing the D1 examination), and collect the diary card on D28 ± 2 days.
- 5) Record AEs: all adverse events should be recorded in the diary cards (if the subjects continue to be hospitalized, adverse events will be recorded in the hospitalization medical record).
- 6) Record concomitant medications: all concomitant medications should be recorded in the diary card (if the subjects continue to be hospitalized, concomitant medications related to primary tumor treatment can be recorded in the hospitalization doctor's order, and medications taken on their own or for long-term underlying diseases can be recorded in the diary cards).
- 7) Trial completion: the study will be completion for subject after the relevant procedures on D28 ± 2d. Subject should be permitted to undergo relevant chemotherapy, radiotherapy and/or immunotherapy for the primary disease during the safe follow-up period.

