15. Enrollment: The subjects were enrolled after reviewing the inclusion and exclusion criteria on D-1 again, and were hospitalized in the department of primary tumor due to primary tumor before D-1 and after D1. After the end of the trial period of this clinical trial, the possible continued hospitalization of the subjects was not affected.(Note: Researchers can arrange for subjects to enter a safe follow-up period based on their condition, after completing the collection of tissue specimens (D2) or surgical specimens (D2-D5) during the trial period, or after completing various operations in D1 for subjects who do not need to collect new tissue specimens, to shorten the waiting time for subsequent treatment from an ethical perspective.)
16. Concomitant Medications: Starting from the signing of the informed consent form, record the daily concomitant medication until the end of the trial. (For subjects who are no longer hospitalized, the safe follow-up period will be recorded in the diary card; if they continue to be hospitalized, the combination medication will be reflected in the hospitalization doctor's order, and drugs taken on their own or for underlying diseases for a long time can be recorded in the diary card).
17. AE: Record any AE observed by the subjects after administration until the end of the experiment. (For subjects who are no longer hospitalized, the safe follow-up period shall be recorded in the diary card; if hospitalization continues, adverse events shall be recorded in the hospitalization medical record).
18. Premature Withdrawal: For subjects who withdraw prematurely, laboratory tests such as vital signs, 12-lead ECG, blood routine, blood biochemistry, coagulation and electrolytes should be performed (if the subject withdraws after D6, and laboratory tests and 12-lead ECG have been performed on D6, they can no longer be performed), anti-SNA002 anti-drug antibody tests should be performed, and adverse events and concomitant medications of the subjects should be recorded.

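### The SAE definition has no limb for medically important events, so a reaction treated within an existing tumour admission without prolonging it is not serious, while the same reaction that admits an outpatient is

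*Combined protocol and SAP*

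**What the plan says.** Section 8.1.2 defines an SAE by a closed list. It opens with "adverse medical events that lead to death, life-threatening results, permanent or serious disability or loss of function" and closes with "or hospitalization or prolonged hospitalization in the subjects after receiving the investigational drug or congenital abnormalities or birth defects". Nothing else in section 8 adds a limb for events judged medically important.

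Admission status differs between subjects by design:

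- 7.3.2 (Baseline Period): "Subjects can be enrolled in the relevant department due to primary tumor before D-1 and after D1 and complete the trial period during hospitalization".
- The enrollment note under Table 4 (7.3.7) says that subjects "were hospitalized in the department of primary tumor due to primary tumor before D-1 and after D1".
- 7.3.4 also provides for outpatients: "if the subjects are not hospitalized, the diary cards will be issued after completing the D1 examination".

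Four parts of the plan use seriousness:

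- 4.2 makes the incidence of TEAEs and SAEs a primary endpoint.
- 5.4 calls for termination if more than half of subjects have related events of grade 2 or above, "or if one case of investigational drug-related SAE is observed".
- 6.1.7.2 lists three triggers for stopping escalation, the third being "or one serious adverse reaction in certain group".
- 8.4.2 requires the investigator to report SAEs to the sponsor within 24 h.

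**The concern.** A reaction that is not fatal, life-threatening, disabling or congenital has only one route to seriousness, which is that it causes or lengthens a hospital stay. A subject already on the ward for the tumour cannot be admitted again. If the reaction is treated there and the stay is no longer than it would have been, the event is not an SAE. If the same reaction leads to the admission of an outpatient, it is.

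This bears on the reaction the plan itself expects. The dose escalation criteria in the Protocol Summary name infusion-related reactions as the likely main safety risk and call them medically manageable. Such reactions will often fall outside the death and disability limbs, so their seriousness can turn on the hospitalization limb.

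At stake are a component of the primary endpoint, two rules that fire on one event, and the 24 h report.

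**Working it through.** **Planned size.** The Protocol Summary gives four dose levels and 10.5 gives 3 to 7 subjects per group. 4 × 3 = 12 and 4 × 7 = 28, which reproduces the stated 12–28.

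**Effect on SAE incidence.** One event moved in or out of the SAE count changes the overall incidence by 1/28 = 3.6 percentage points at the largest size and 1/12 = 8.3 points at the smallest.

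**Whether another escalation rule catches the same single event.** In 6.1.7.2 the first trigger is at least half of the group at grade 2 or above, and the second is at least one third at grade 3 or above. For a group of n, the subjects needed are n/2 and n/3, rounded up:

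| n | Grade 2 rule | Grade 3 rule | Serious-reaction rule |
|---|---|---|---|
| 3 | 2 | 1 | 1 |
| 4 | 2 | 2 | 1 |
| 5 | 3 | 2 | 1 |
| 6 | 3 | 2 | 1 |
| 7 | 4 | 3 | 1 |

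One reaction classed as non-serious still stops escalation in a group of 3, provided it is graded 3 or above. In groups of 4 to 7 it does not; in a group of 7 it is 1/7 = 14%, against a limit of one third.

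The trial-level rules do not catch it either. Section 5.4 has no grade 3 criterion. Its grade 2 criterion needs more than half of subjects, and 8.5 needs three grade 2 events.

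**Whether grading is independent of admission.** Not fully. In 8.2.1 the severe category includes events that cause hospitalization or a longer stay, so the second trigger can carry part of the same dependence.

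**Illustration of the escalation stop.** The documents give neither of two quantities, so both are assumptions:

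- p is the rate per subject of a drug-related reaction that would lead to admission but meets no other limb.
- f is the share of subjects already admitted whose stay the reaction would not prolong.

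With independent subjects, the chance that the one-serious-reaction stop fires is 1 − (1 − p(1 − f))^n. For example, with p = 0.05, f = 0 and n = 7, it is 1 − 0.95^7 = 30%.

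| p | n | f = 0 | f = 0.5 | f = 1 |
|---|---|---|---|---|
| 0.05 | 3 | 14% | 7% | 0% |
| 0.05 | 7 | 30% | 16% | 0% |
| 0.10 | 3 | 27% | 14% | 0% |
| 0.10 | 7 | 52% | 30% | 0% |
| 0.20 | 3 | 49% | 27% | 0% |
| 0.20 | 7 | 79% | 52% | 0% |

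A definition that does not depend on admission status gives the f = 0 column for any mix of subjects. The figures are for the seriousness rule alone; for n = 3 the grade 3 rule is a back-up as described above.

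**The case against.** The strongest reply is that the gap is small and partly covered. Several parts of it stand.

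- **Most limbs do not depend on admission.** A reader might infer that seriousness turns entirely on where the subject was staying. The documents do not support that. Fatal, life-threatening, disabling and congenital events are SAEs in any setting, and the prolonged-stay limb is written for people already admitted. A D1 reaction that delays biopsy, surgery or discharge would count.
- **A reaction needing emergency treatment is a poor example.** 8.2.1 places emergency treatment in the life-endangering category, and such an event would meet the life-threatening limb whatever the admission status.
- **An outpatient kept overnight is not clearly an SAE.** The plan does not define an overnight stay as hospitalization, and the Protocol Summary already has every patient observed at 6±1 h and 24±6 h. The contrast holds for an outpatient who is actually admitted.
- **The event is not lost.** It is recorded and graded as an AE (8.3, 8.4.1) and counts in TEAE incidence, which is part of the same primary endpoint. The principal investigator decides on escalation, a safety committee has oversight (8.6), and 8.4.3 has the sponsor assess safety information from any source.

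These points limit the size of the problem but do not close it. None of them makes the event an SAE, starts the 24 h clock in 8.4.2, or fires the single-event rule in 5.4 or, in groups of 4 to 7, the one in 6.1.7.2. Discretion may lead to the same action, but it is not the rule as written.

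**Conclusion.** The point holds in a narrow form. Following 8.1.2 as written, a reaction that would admit an outpatient, is treated within an existing tumour stay without prolonging it, and meets no other limb is not an SAE. This follows from the plan's own text and needs no outside definition of seriousness.

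The consequence of one such event is definite: it changes SAE incidence by 3.6 to 8.3 percentage points and decides whether the single-event rules fire. The frequency is unknown, because neither the inpatient share nor the reaction rate is given; the probabilities above are illustrations.

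A reader might infer that the problem disappears if all subjects are inpatients. Only the inconsistency between subjects would disappear. Under-capture would then be greatest, and in the limiting case f = 1 the stop never fires for these reactions. This is an inexpensive improvement that should be made.

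**What to change.** Amend 8.1.2 in three respects:

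1. Add that an event is also serious if the investigator judges it medically important. This includes an event that would have led to admission in a subject not already in hospital, or that needed intervention to prevent one of the listed outcomes.
2. State that admissions or stays planned before dosing for tumour care, biopsy or surgery are not SAEs in themselves.
3. State that this one definition applies wherever 5.4, 6.1.7.2 and 8.4.2 refer to SAEs or serious reactions, with the thresholds in those sections left as they are.

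The cost is a few sentences in 8.1.2 and a matching change to the SAE form. The downside is that slightly more events may be reported as SAEs, which the second item limits.

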8.1.3 Definition Of Unanticipated Problems (UP)

OHRP considers unanticipated problems involving risks to participants or others to include, in general, any incident, experience, or outcome that meets all of the following criteria:

- Unexpected in terms of nature, severity, or frequency given (a) the research procedures that are described in the protocol-related documents, such as the IRB-approved research protocol and informed consent document; and (b) the characteristics of the participant population being studied;
- Related or possibly related to participation in the research (“possibly related” means there is a reasonable possibility that the incident, experience, or outcome may have been caused by the procedures involved in the research); and

- Suggests that the research places participants or others at a greater risk of harm (including physical, psychological, economic, or social harm) than was previously known or recognized.

This study will use the OHRP definition of UP.

Suspected unexpected serious adverse reaction (SUSAR) refers to suspected and unexpected serious medical events with clinical manifestations and severity that are not listed in the existing data or information, such as the investigator's brochure, package inserts of the marketed drugs, or summary of product characteristics.

8.2 Classification Of an Adverse Event

8.2.1 Severity Of Event

- **Mild** – No clinical symptoms or mild clinical symptoms; only clinical or laboratory abnormalities; no treatment required.
- **Moderate** – Requiring minimal, local, or non-invasive treatment; The daily activities of using tools that are appropriate for age are limited, and the daily activities of using tools include cooking, shopping, making phone calls, etc.
- **Severe** –Illness or medically severe symptoms but not immediately life-threatening; Causing hospitalization or prolonged length of stay; Causing disability; Restricted daily self-care. Self care in daily life refers to bathing, dressing, undressing, eating, going to the bathroom, taking medication, etc., not being bedridden.
- Endangering life and requiring emergency treatment.
- Deaths related to AE.

8.2.2 RELATIONSHIP TO STUDY AGENT

Correlation determination can be done using the five point method: relevant, highly likely related, possibly related, possibly unrelated, or unrelated. Dichotomy can also be used: relevant or unrelated (those that are relevant, highly likely related, or possibly related can be classified as "relevant" according to the dichotomy method; those that are unrelated or potentially unrelated can be classified as "unrelated" according to the dichotomy method).

Table 5 Classification and criteria for determining the correlation between adverse events in clinical drug trials

Five point method	Basis of determination	Dichotomy
Related	
 - Has a reasonable temporal relationship -Conforming to known drug mechanisms, characteristics, or known adverse reactions -De-excitation positive -No other plausible explanation -Re-excitation positive 	relevant
Probably	- Has a reasonable temporal relationship	

Related	
 -Conforming to known drug mechanisms, characteristics, or known adverse reactions -De-excitation positive -No other plausible explanation -Absence of Re-excitation positive proof. 	
Possibly Related	
 -Has a reasonable temporal relationship -Absence of re-excitation positive proof -Manifested as any of the following situations: 
 ①Conforming to known drug mechanisms, characteristics, or known adverse reactions, de-excitation positive, but other reasonable reasons can also be used for explanation. ② Conforming to known drug mechanisms, characteristics, or known adverse reactions, absence of de-excitation positive proof, and there are no other reasonable reasons to explain. ③Does not conform to the known mechanism of action, properties or known adverse reactions of the drug, de-excitation positive, and there is no other reasonable reason to explain. ④ Does not conform to the known mechanism of action, properties or known adverse reactions of the drug, de-excitation positive,also explained by other plausible reasons. ⑤ Does not conform to the known mechanism of action, , properties or known adverse reactions of the drug,absence of de-excitation positive proof, and no other plausible reason to explain. 	
Unlikely to be related	
 -Has a reasonable temporal relationship -Absence of de-excitation positive proof -Absence of re-excitation positive proof -Manifested as any of the following situations: 
 ① Does not conform to the known mechanism of action, properties or known adverse reactions of the drug, and can be explained by other reasonable reasons. ②Conforming to known drug mechanisms, characteristics, or known adverse reactions, but other reasonable reasons can be used for explanation. 	unrelated
Not Related	
 - (Medically considered) There is no rational time relationship -Does not conform to the known mechanism of action, properties or known adverse reactions of the drug -Absence of de-excitation positive proof -Absence of re-excitation positive proof -Other reasonable reasons can be used to explain 	

8.2.3 Expectedness

Sponsor will be responsible for determining whether an AE is expected or unexpected. An AE will be considered unexpected if the nature, severity, or frequency of the event is not consistent with the risk information previously described for the study agent

8.3 Time Period and Frequency for Event Assessment and Follow-Up

The occurrence of an AE or SAE may come to the attention of study personnel during study visits and interviews of a study participant presenting for medical care, or upon review by a study monitor. All AEs including local and systemic reactions not meeting the criteria for SAEs will be captured on the appropriate RF. Information to be collected includes event description, time of onset, clinician's assessment of severity, relationship to study product (assessed only by those with

the training and authority to make a diagnosis), and time of resolution/stabilization of the event. All AEs occurring while on study must be documented appropriately regardless of relationship. All AEs will be followed to adequate resolution.

Any medical condition that is present at the time that the participant is screened will be considered as baseline and not reported as an AE. However, if the study participant's condition deteriorates at any time during the study, it will be recorded as an AE. UPs will be recorded in the data collection system throughout the study.

Changes in the severity of an AE will be documented to allow an assessment of the duration of the event at each level of severity to be performed. AEs characterized as intermittent require documentation of onset and duration of each episode.

The PI will record all reportable events with start dates occurring any time after informed consent is obtained until 7 (for non-serious AEs) or 30 days (for SAEs) after the last day of study participation. At each study visit, the investigator will inquire about the occurrence of AE/SAEs since the last visit. Events will be followed for outcome information until resolution or stabilization

8.4 Reporting Procedures

8.4.1 Adverse Event Reporting

All AEs occurring after the first dose and before the last follow-up need to be collected and recorded. If an AE occurs after the last follow-up (within one month after the follow-up) and it cannot be determined as unrelated to the investigational drug, then the follow-up should be continued and recorded for this case until symptom disappearance or recovery to the baseline (or even better than the baseline), or disease stability, or the recovery of any laboratory abnormalities to normal or the baseline level, or loss to follow-up. The AE record form should be authentically filled out during the trial, including AE's name, time of occurrence, severity, end time, relevance to the investigational drug, countermeasures, and outcome.

All AEs (including SAEs/SUSARs) occurring during the clinical trial will be graded according to the severity classification system for AEs in Chapter 8.1.3 and then properly handled. Whether there is a causal relationship between an AE and the investigational drug, the investigators should carry out a follow-up of the AE until symptom disappearance or recovery to the baseline (or even better than the baseline), or disease stability, or the recovery of any laboratory abnormalities to normal or the baseline level, or loss to follow-up. For clinically significant laboratory abnormalities of grade 3 or 4, close follow-up and reexamination should be carried out.

During the follow-up of AEs, the cases progressing into SAEs should be reported following the SAE reporting procedures after the investigators are informed of the situation.

The investigators should observe and treat the AEs based on clinical practice and prepare original medical records during the treatment.

